5 STUDY DESIGN

5.1 Overall Design

This randomized, open-label Phase 2 study was to evaluate whether the combination of nivolumab, with abemaciclib or palbociclib, plus anastrozole is a safe and effective neoadjuvant treatment for men and postmenopausal women with primary BC ≥ 2 cm that is ER+ and HER2- subtype who are suitable to receive NET and willing to undergo SOC breast surgery after completion of the study treatment.

On 6-Mar-2020, Bristol Myers Squibb (BMS) decided to permanently discontinue enrollment and dosing in the nivolumab + abemaciclib + anastrozole cohorts of the CA2097A8 study during the Safety Run-in Phase.

At implementation of Revised Protocol 03, the study will only evaluate whether the combination of nivolumab, with palbociclib, plus anastrozole is a safe and effective neoadjuvant treatment for men and postmenopausal women with primary BC ≥ 2 cm that is ER+ and HER2- subtype who are suitable to receive NET and willing to undergo SOC breast surgery after completion of the study treatment. Participants must have histologically confirmed invasive breast carcinoma meeting the characteristics described in [Section 6.1](#) (Inclusion Criteria). Participants in screening and not yet treated were offered the option to join the safety lead-in of the nivolumab + palbociclib + anastrozole arm. Participants on treatment with nivolumab + abemaciclib + anastrozole were to be re-consented and continue on anastrozole alone, OR taken off study. In addition, baseline chest X-ray and periodic pulse oximetry are implemented to monitor ILD/pneumonitis in patients who will be treated with nivolumab + palbociclib + anastrozole.

The study is divided into 3 periods: Screening Period, On-treatment Pre-surgery (neoadjuvant) Period (Safety Run-in Phase and Randomized Phase), and Safety Follow-up Period.

The study started with a Safety Run-in Phase for the combination of nivolumab, with abemaciclib or palbociclib, plus anastrozole and will begin the Randomized Phase after the regimen is determined to be safe. Participants in the Safety Run-in Phase will move to the Safety Follow-up Period upon completion of the neoadjuvant treatment or upon discontinuation. Potential needs for additional enrollment or for dose de-escalation will be discussed with Investigators and BMS during the Safety Run-in Phase. Once a safe dose for the regimen has been determined by BMS in collaboration with Investigators, the Randomized Phase of the study will begin.

[figure not shown]
In the Randomized Phase, participants will be randomly assigned by an IRT system to 3 different treatment arms and stratified by the following factors:

2) evaluation of lymph nodes (cytologically positive vs radiologically or cytologically negative); and 3) tumor size (> 3 cm or ≤ 3 cm).

For both the Safety Run-in Phase and Randomized Phase, participants will be treated for a maximum of 5 cycles (1 cycle = 4 weeks). Participants with progressive disease prior to completion of the 5-cycle study treatment must discontinue all study drugs and proceed to the Safety Follow-up Period. Participants who permanently discontinue the study drugs for any reason are considered to have completed the On-treatment Pre-surgery (neoadjuvant) Period, and hence reach end of treatment (EOT). After Cycle 5 or EOT, participants must continue to receive anastrozole (as concomitant medication and not as study treatment) until subsequent SOC breast surgery. Following the completion of neoadjuvant treatment, all participants who remain operative candidates will undergo definitive surgery for BC within 4 weeks of the last neoadjuvant treatment administration. If anastrozole can no longer be administered after EOT, participants will go to breast surgery right away. Pre-surgical lymph node biopsy is not allowed. Information on the type of the surgery will be collected and recorded in the electronic case report form (eCRF). Surgical specimens will be collected for the analyses outlined in the protocol. Depending on treatment assignment, up to 2 safety follow-up visits will be conducted in person. The first safety follow-up visit (FU1) will be completed for all participants within 30 days (± 7 days) from the last study treatment (oral or intravenous [IV], whichever occurs later). The second safety follow-up visit (FU2) will occur approximately within 100 days (± 7 days) from the last dose of nivolumab and will be required for participants in the Safety Run-in Phase and participants randomized to Arms A or B in the Randomized Phase. Further planned treatment of participants in the adjuvant setting (ie, radiotherapy, endocrine treatment, chemotherapy or any other treatment modality) will be at the discretion of the treating physician, following local clinical guidelines, and collected in the appropriate eCRF.

The study design schematic is presented in [Figure 5.1-1](#).

Figure 5.1-1: Study Design Schematic

Abbreviations: Abema = abemaciclib; ANZ = anastrozole; BID = twice daily; cm = centimeter; ECOG = Eastern Cooperative Oncology Group; ER+ = estrogen-receptor-positive; FU1 = follow-up visit 1; FU2 = follow-up visit 2; HER2- = human epidermal growth factor receptor 2-negative; IV = intravenous; mg = milligram; N = number; Nivo = nivolumab; Palbo = palbociclib; PO = per os (by mouth); PS = performance status; Q4W = every 4 weeks; QD = once daily; Rand = randomized; wk = week.

^a FU1 begins at the end of study treatment.

^b Cytologically positive vs radiologically or cytologically negative.

- ^c At the time of Revised Protocol 03, 2 participants had been treated in Cohort 1 (nivolumab + abemaciclib + anastrozole), which was subsequently closed for enrollment.
- ^d At time of Revised Protocol 03, the decision was made to no longer evaluate abemaciclib in combination with nivolumab plus anastrozole; thus, the abemaciclib-containing combination arms have been removed from the Randomization Phase of the study.

5.1.1 Screening Period

Participants will provide written informed consent to participate in the study before completing any protocol-specified procedures or evaluations not considered to be part of the participants' standard care. After signing the informed consent form (ICF), participants will be evaluated for entry criteria and be enrolled into Interactive Response Technology (IRT). The screening assessments are shown in [Table 2-1](#).

Participants must provide a pretreatment (baseline) tumor tissue, which must be either in FFPE tissue block containing 20 mm³ of tissue collected ≤ 90 days prior to enrollment (strongly preferred) or unstained tumor tissue sections (22 unstained slides) sectioned ≤ 60 days prior to enrollment from a tissue sample collected ≤ 90 days prior to enrollment from primary tumor lesion. If a recent tumor specimen is not available, a fresh tumor biopsy (containing 20 mm³ of tissue) is required. At least 15 unstained slides must be submitted for a participant to be eligible. If < 15 unstained slides are available, the participant is not eligible. Submit samples to the designated central laboratory with an associated pathology report. [REDACTED]

Safety Run-in participants: Participant can start study treatment before confirmation of receipt of the tumor sample by the central laboratory. However, receipt of the tumor sample by the central laboratory must occur within 28 days of the first dose.

Randomized participants: [REDACTED]
[REDACTED] Documentation of tumor size and node status (cytologically positive vs radiologically or cytologically negative) must be provided to IRT prior to randomization.

[REDACTED]

The Screening Period for each participant ends with the confirmation of full eligibility of the participant or with the confirmation that the participant is a screen failure. This study permits the re-enrollment of a participant that has discontinued the study as a pretreatment failure (ie, participant has not been randomized [or treated in the Safety Run-in Phase]). If re-enrolled, the participant must be re-consented.

5.1.2 On-treatment Pre-surgery (neoadjuvant) Period

A schedule of on-treatment visits and assessments is provided in [Table 2-2](#).

5.1.2.1 Safety Run-in Phase

As of Revised Protocol 03, Cohort 1 will be discontinued. Participants in screening and not yet treated were offered the option to join the nivolumab + palbociclib + anastrozole arm. Participants on treatment were to be re-consented and continue on anastrozole alone, OR taken off study.

The Safety Run-in Phase will be conducted in advance of the Randomized Phase to evaluate the safety and tolerability of the combination of nivolumab, with palbociclib, plus anastrozole, which will be administered during the Randomized Phase.

Participants will receive palbociclib in combination with nivolumab plus anastrozole (Cohort 2) for 5 cycles as neoadjuvant therapy and be followed up for safety (see [Section 5.1.3](#) [Safety Follow-up Period]). For the purpose of guiding alternative dose levels, all AEs will be graded according to the National Cancer Institute (NCI) Common Terminology Criteria for Adverse Events (CTCAE) v5.0 and dose-limiting toxicities (DLTs) will be defined based on the incidence, intensity, and duration of the AEs for which no clear alternative cause is identified. For the purpose of participant management, any drug-related AE that meets DLT criteria will lead to discontinuation of study treatment.

Participants who have discontinued due to a DLT or who have received 1 dose of nivolumab and 75% of accumulative doses of palbociclib of the cycle, and have completed the 4-week DLT period will be considered as DLT-evaluable participants. Participants who withdraw from the study during the DLT evaluation period or have received less than 1 dose of nivolumab and 75% of accumulative doses of palbociclib of the cycle for reasons other than a DLT will not be considered as DLT-evaluable participants and may be replaced with new participants at the same dose level.

[figure not shown]
Dose De-escalation Rules

For Cohort 2, 3 DLT-evaluable participants will be treated with the below starting doses:

- Nivolumab: 480 mg every 4 weeks (Q4W) intravenously (IV)
- Palbociclib 125 mg once daily (QD) PO for 3 weeks of each cycle (1 week off)
- Anastrozole: 1 mg QD PO

If no participants (0 of 3 DLT-evaluable participants) experience a DLT during the DLT period (4 weeks), the Randomized Phase will be initiated at this dose level. If 1 evaluable participant (1 of 3 DLT-evaluable participants) experiences DLT, then the cohort will be expanded to 6 DLT-evaluable participants. If no more DLTs are observed (1 of 6 DLT-evaluable participants), then the Randomized Phase will be initiated at the dose level tested. If 1 or more additional evaluable participants (2 of 6 DLT-evaluable participants) experiences DLT during the DLT period, a lower dose will be tested using the same 3 + 3 schema. See [Figure 5.1.2.1-1](#) for an overview of the 3 + 3 approach to be used for the Safety Run-in Phase.

Figure 5.1.2.1-1: Schematic of Safety Run-in Phase 3 + 3 Approach

Abbreviations: DLT = dose-limiting toxicity.

^a For additional details see [Section 7.4](#) (Dosage Modification).

Continuous evaluation of toxicity events will be performed. If at any time, the aggregate rate of treatment-related toxicities meeting DLT criteria exceeds 33% across participants treated in a cohort, the findings will be discussed with the Investigators and further enrollment may be interrupted. Any toxicities that occur beyond the DLT period will be accounted for in making final dose level decisions.

Generally, if a cohort is discontinued due to DLT of unclear relevance to nivolumab, a lower dose level of CDK4/6 inhibitor per product label will be tested in the next cohort. See [Section 7.4](#) (Dosage Modification) for additional details on permitted dose adjustment. If a cohort is discontinued due to DLT related to nivolumab, a different dose or dose schedule will be explored per Investigator and Medical Monitor discussion.

For cohort expansion or dose de-escalation decisions, the available toxicity information (including AEs and laboratory abnormalities that are not DLTs), clinical judgment [REDACTED] will be evaluated by the Investigators and BMS study personnel (including the Medical Monitor and statistician) during a dose decision meeting by teleconference. Drug administration at the next dose level or proceeding to the Randomized Phase must not occur until the Investigator receives written confirmation from BMS indicating that the results of the previous dose level were evaluated and that it is permissible to proceed.

Definition of DLTs: DLTs are defined as any TEAEs specified below that occur during the first 4 weeks (1 cycle) except those clearly and incontrovertibly due to disease progression or extraneous causes.

Gastrointestinal DLTs

- Grade 2 colitis that lasts longer than 7 days, despite best supportive treatment.
- Grade 3 diarrhea or colitis that lasts longer than 72 hours with adequate supportive treatment.
- Grade ≥ 4 diarrhea or colitis.

Hepatic DLTs

- Grade 4 elevations in serum transaminases (aspartate aminotransferase [AST] and alanine aminotransferase [ALT], alkaline phosphatase [ALP]) or total bilirubin.
- Grade 3 elevations in serum AST, ALT, or bilirubin.
- Bilirubin $> 2 \times$ upper limit of normal (ULN) in the absence of cholestasis.
- Grade 2 elevations in AST or ALT with symptomatic liver inflammation (eg, right upper quadrant tenderness, jaundice).
- Grade 3 ALP elevation that last longer than 5 days, or is associated with clinical symptoms.
- AST or ALT $> 3 \times$ ULN and concurrent total bilirubin $> 2 \times$ ULN without initial findings of cholestasis (elevated ALP; eg, findings consistent with Hy's law or FDA definition of potential drug-induced liver injury [p-DILI]). Note that this specific category of DLT uses ULN rather than NCI CTCAE grade for definition.

Hematologic DLTs

- Grade 4 neutropenia ≥ 7 days in duration.
- Grade 4 thrombocytopenia.
- Grade 3 thrombocytopenia with bleeding or any requirement for platelet transfusion.
- Grade 3 hemolysis (ie, requiring transfusion or medical intervention such as steroids).
- Neutropenic fever of any duration.
- Grade 4 anemia not explained by underlying disease.

Dermatologic DLTs

- Grade 4 rash or confirmed Stevens-Johnson Syndrome or Toxic Epidermal Necrolysis.
- Grade 3 rash if no improvement (ie, resolution to \leq Grade 1) after a 1- to 2-week infusion omission for nivolumab.

Other DLTs

- Recurrence of same Grade 3 adverse reactions.

- Any AE that required discontinuation of nivolumab per approved label.
- Any Grade immune-related encephalitis.
- Any incidence of Grade ≥ 3 prolongation of QT interval corrected using Fridericia's Correction Formula (QTcF) on electrocardiograms (ECGs). Grade 3 hypersensitivity reaction/infusion reaction that does not resolve to Grade 1 in < 6 hours.
- Grade 2 pneumonitis that does not respond to dose modification for nivolumab and systemic steroids within 14 days.
- Any death not clearly due to the underlying disease or extraneous causes.
- Grade 2 uveitis, episcleritis, iritis, eye pain, or blurred vision that does not respond to topical therapy and does not improve to Grade 1 severity within 2 weeks OR requires systemic treatment.
- Grade ≥ 3 electrolyte abnormality associated with clinical symptoms.
- Grade 3 fatigue lasting ≥ 1 week.
- Other Grade 3 \geq toxicity will be considered a DLT, except those clearly and incontrovertibly due to disease progression and extraneous causes. However, the following Grade 3 or 4 events will not be considered DLTs:
 - Isolated Grade 3 or 4 electrolyte imbalances/abnormalities not associated with clinical symptoms and either resolve spontaneously or are corrected with supplementation/appropriate management within 72 hours of their onset. Confirmatory laboratory test is required within 72 hours.
 - Grade ≥ 3 amylase or lipase elevation not associated with symptoms or clinical manifestations of pancreatitis.
 - Grade 3 nausea or vomiting that lasts less than 48 hours and either resolves spontaneously or responds to medical intervention.
 - Grade 3 fever not associated with hemodynamic compromise (eg, hypotension, clinical or laboratory evidence of impaired end-organ perfusion).
 - Grade 3 endocrinopathy that is well controlled by hormone replacement.
 - Grade 3 tumor flare (defined as pain, irritation, or rash that localizes to sites of known or suspected tumor).

5.1.2.2 **Randomized Phase**

The Randomized Phase will start after the combinations tested in the Safety Run-in Phase are confirmed to be safe by BMS in collaboration with Investigators, and the appropriate dose level communicated to Investigators. Following confirmation of eligibility criteria, participants will be randomized to either Arm A, Arm B, or Arm C in a 4:4:3 ratio, respectively. Participant randomization will be stratified using the following factors:

- 2) Evaluation of lymph nodes (cytologically positive vs radiologically or cytologically negative), and
- 3) Tumor size (> 3 cm or ≤ 3 cm).

Treatment must begin within 3 calendar days following randomization.

Participants will be randomly assigned to 1 of the 3 treatment arms below:

As of Revised Protocol 03, the abemaciclib-containing combination arms have been removed from the randomization phase of the study.

- 1) Arm A (concurrent palbociclib treatment arm): nivolumab 480 mg Q4W IV + palbociclib 125 mg QD PO for 3 weeks (1 week off) + anastrozole 1 mg QD PO for 5 cycles
- 2) Arm B (phased palbociclib treatment arm):
 - a) palbociclib 125 mg QD PO for 3 weeks of each cycle (1 week off) + anastrozole 1 mg QD PO for 1 cycle followed by
 - b) nivolumab 480 mg Q4W IV + palbociclib 125 mg QD PO for 3 weeks (1 week off) + anastrozole 1 mg QD PO for 4 cycles
- 3) Arm C (control palbociclib arm): palbociclib 125 mg QD PO for 3 weeks of each cycle (1 week off) + anastrozole 1 mg QD PO for 5 cycles

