8.1.1 Nivolumab Dose Discontinuation

If a participant discontinues nivolumab, the entire study treatment (CDK4/6 inhibitor and anastrozole) must be discontinued.

Nivolumab treatment should be permanently discontinued for the following:

- Any Grade 2 drug-related uveitis, eye pain, or blurred vision that does not respond to topical therapy and does not improve to Grade 1 severity within the re-treatment period OR requires systemic treatment.
- Any Grade 3 non-skin, drug-related AE lasting > 7 days or recurs, with the following exceptions for laboratory abnormalities, drug-related uveitis, pneumonitis, bronchospasm, neurologic toxicity, hypersensitivity reactions, infusion reactions, and endocrinopathies:
 - Grade 3 drug-related uveitis, pneumonitis, bronchospasm, neurologic toxicity, myocarditis, hypersensitivity reaction, or infusion reaction of any duration requires discontinuation.
 - Grade 3 drug-related endocrinopathies, adequately controlled with only physiologic hormone replacement do not require discontinuation. Adrenal insufficiency requires discontinuation regardless of control with hormone replacement.
 - Grade 3 drug-related laboratory abnormalities do not require treatment discontinuation except:
 - ◆ Grade 3 drug-related thrombocytopenia > 7 days or associated with bleeding requires discontinuation.
 - ◆ Grade ≥ 3 drug-related AST, ALT, or total bilirubin requires discontinuation (see below).
 - ◆ Concurrent AST or ALT > 3 \times ULN and total bilirubin > 2 \times ULN.

NOTE: In most cases of Grade 3 AST or ALT elevation, study treatment will be permanently discontinued. If the Investigator determines a possible favorable benefit-risk ratio that warrants continuation of study treatment, a discussion between the Investigator and the Medical Monitor/designee must occur.

- Any Grade 4 drug-related AE or laboratory abnormality (including, but not limited to, creatinine, AST, ALT, or total bilirubin), except for the following events which do not require discontinuation:
 - Grade 4 neutropenia ≤ 7 days.
 - Grade 4 lymphopenia or leukopenia or asymptomatic amylase or lipase elevation.
 - Isolated Grade 4 electrolyte imbalances/abnormalities that are not associated with clinical sequelae and are corrected with supplementation/appropriate management within 72 hours of their onset.

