**Table 6.3-1: Populations for Analyses**

Population	Description
All Enrolled	All participants who signed an ICF and were registered into the IRT.
All Randomized	All participants who were randomized to any treatment arm in the study. Participants are grouped within the All Randomized population by the treatment to which they were randomized.  This is the primary analysis set for demography, protocol deviations, baseline characteristics, and primary efficacy analyses.
All Treated	All randomized participants who receive at least 1 dose of study drug. Participants are grouped within the All Treated population according to the treatment they actually received. This is the analysis set for all safety analyses and study drug administration.
All Treated from Safety Run-in Phase	All enrolled participants who received at least 1 dose of study drug in the Safety Run-in Phase. Participants are grouped within the All Treated from Safety Run-in Phase population according to the treatment and dose level they actually received. This is part of the analysis set for all safety analysis and study drug administration.
All DLT-Evaluable	All participants treated in Safety Run-in Phase who have discontinued due to a DLT or who have received 1 dose of nivolumab and 75% of accumulative doses of abemaciclib or palbociclib of the cycle, and have completed the 4-week DLT period.
All RCB Evaluable	All Treated participants who have an RCB of 0, I, II, or III from both the Safety Run-in Phase and Randomized Phase.

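### The run-in stopping rule for DLTs and Section 8.1.1 allow different actions for some of the same events, and DLT-evaluability turns on whether treatment was stopped

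*Protocol*

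**What the plan says.** **Stopping rules.** Protocol 5.1.2.1 (Safety Run-in Phase) says that, for participant management, "any drug-related AE that meets DLT criteria will lead to discontinuation of study treatment". The DLT list there names "Grade 3 elevations in serum AST, ALT, or bilirubin" and Grade 4 neutropenia lasting 7 days or more. It closes with a residual line: other Grade 3 or higher "toxicity will be considered a DLT, except those clearly and incontrovertibly due to disease progression and extraneous causes". Six exceptions follow. Leukopenia and lymphopenia have no line of their own and are not among the six.

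Protocol 8.1.1 sets out when nivolumab is stopped, and stopping nivolumab stops all study treatment. It says "Grade 3 drug-related laboratory abnormalities do not require treatment discontinuation except" for certain platelet and liver findings. A note on Grade 3 AST or ALT elevation says treatment is stopped in most cases, but adds: "If the Investigator determines a possible favorable benefit-risk ratio that warrants continuation of study treatment", a discussion with the Medical Monitor must take place. Its list of Grade 4 events that do not require stopping includes neutropenia of 7 days or less and "Grade 4 lymphopenia or leukopenia or asymptomatic amylase or lipase elevation".

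**Evaluability.** SAP Table 6.3-1 counts as DLT-evaluable those run-in participants "who have discontinued due to a DLT or who have received 1 dose of nivolumab and 75% of accumulative doses of abemaciclib or palbociclib" for the cycle and completed the 4-week period. Protocol 5.1.2.1 gives the same two routes for palbociclib. It adds that participants who withdraw, or who receive less than the required dosing "of the cycle for reasons other than a DLT will not be considered as DLT-evaluable participants" and may be replaced. The 3+3 rule counts DLT-evaluable participants.

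**The concern.** The same run-in participant can fall under two stated rules. One makes stopping mandatory. The other leaves room to continue, or does not require stopping. Section 8.1.1 is not limited to the Randomized Phase, and the heading of Section 7.1.1 on nivolumab dosing names the run-in cohorts. Neither 5.1.2.1 nor 8.1.1 cites the other. Section 7.4 says that events requiring discontinuation must lead to it, but not which list decides.

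The statistical consequence comes through evaluability. The first route asks whether the participant discontinued because of a DLT, not whether a DLT occurred. If a site keeps a participant with a DLT on treatment under 8.1.1 and palbociclib is interrupted, which Section 7.4.2 permits, an observed DLT may not enter the written tally that decides whether the Randomized Phase opens at that dose. That tally rests on 3 to 6 participants.

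**Working it through.** **Plan size.** The stated total of 115 to 136 treated is the only size that includes the run-in. It reproduces as 110 + 2 + 3 = 115 and 110 + 2 + 24 = 136. Nothing here changes it.

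**Step 1: the two rules side by side.**

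| Drug-related event in first 4 weeks | Protocol 5.1.2.1 | Protocol 8.1.1 |
|---|---|---|
| Grade 3 AST or ALT elevation | Named DLT: stop | Stop in most cases; may continue after Medical Monitor discussion |
| Grade 4 neutropenia, exactly 7 days | DLT (≥ 7 days): stop | Stopping not required (≤ 7 days) |
| Grade 3–4 leukopenia or lymphopenia, recorded as an AE | DLT if the residual line reaches it: stop | Stopping not required |

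The first two rows need no interpretation of the residual line. The third does, and it also needs the laboratory result to be an AE. Section 9.2.6 makes it one if it is clinically significant or serious, led to treatment being interrupted or stopped, or needed specific corrective therapy.

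**Step 2: the dosing threshold.** Palbociclib is taken once daily for 3 weeks of each cycle, so Cycle 1 has 3 × 7 = 21 doses. SAP Table 7.4.1-2 also uses 21 of 28 days.

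- 0.75 × 21 = 15.75, so at least 16 doses are needed.
- 16/21 = 76.2% meets the threshold; 15/21 = 71.4% does not.
- 21 − 15 = 6, so 6 or more missed doses fall short.

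**Step 3: who is left unclassified.** Take a participant with a DLT who stays on treatment and takes 15 doses.

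- Discontinued because of a DLT: no.
- One nivolumab dose, 75% of palbociclib and 4 weeks completed: no, 71.4%.
- Excluded and replaceable under 5.1.2.1: no, if the shortfall is due to the DLT, because that sentence covers only other reasons.

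The protocol therefore neither includes nor excludes this participant. The SAP definition leaves the participant out. With 16 or more doses and the 4 weeks completed, the participant is evaluable either way and the gap does not arise.

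**Step 4: the tally.** The written rule is: 0 of 3, start; 1 of 3, expand to 6; 1 of 6, start; 2 of 6, test a lower dose. Suppose one of the first three participants has a Grade 3 ALT elevation and 6 missed palbociclib doses, and the other two have no DLT.

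- Treatment stopped under 5.1.2.1: 1 of 3, so the cohort is expanded.
- Treatment continued under the 8.1.1 note: 0 DLTs among 2 evaluable participants. The rule needs 3, and no text provides for replacing the third.

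In an expanded cohort with one DLT already counted, the same loss leaves 1 of 5 evaluable where the full tally would be 2 of 6. Again the rule has no entry for that count.

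**Step 5: what does not change.** SAP 7.6 tabulates safety for all treated subjects unless otherwise specified. SAP 7.6.1 summarises DLTs by cohort and dose level, with a listing for all treated subjects. Neither restricts the report to DLT-evaluable participants.

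The documents give no Grade 3–4 rates for these events in this combination, so no probability is attached.

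**The case against.** The strongest reply is that 5.1.2.1 is the specific run-in rule and 8.1.1 a general minimum. Not requiring discontinuation does not forbid it, so a site that stops complies with both. **This stands for leukopenia and lymphopenia.** A reader might infer that the two sections give opposite orders there, but the text shows only a missing cross-reference and an unclear reach of the residual line. It stands less well for AST and ALT, because the 8.1.1 note expressly contemplates continuing study treatment. Still, 8.1.1 itself stops treatment in most such cases, so the exception is narrow, and the neutropenia overlap is a single day.

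Second, the evaluability gap arises mainly when 5.1.2.1 is not followed, and it also needs at least 6 missed doses. That is correct and keeps the case uncommon. It does not supply the missing rule.

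Third, other safeguards exist. The 33% trigger in 5.1.2.1 counts treated participants: 1 of 3 is 33.3%, so the example above would already prompt discussion with the investigators. The dose decision meeting weighs all toxicity and clinical judgment, and written sponsor confirmation is required before proceeding. These stand and limit the harm.

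A reader might also infer a clash between the symptomatic electrolyte DLT and the electrolyte exception. There is none: the exception covers only events without clinical symptoms.

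**Conclusion.** The point holds as a **minor** inconsistency. For Grade 3 AST or ALT elevation and for Grade 4 neutropenia of exactly 7 days, two current passages allow different actions for the same run-in participant, and no visible text ranks them. Separately, the evaluability definition can leave one observed DLT out of a tally of 3 to 6. That requires the participant to stay on treatment with 15 or fewer of 21 doses, or not to complete the 4-week period.

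Two stronger readings are tempting and not supported. One is that the run-in primary endpoint would be misreported. That endpoint is the number of participants with a DLT, and the SAP tabulates and lists DLTs for treated subjects, so only the 3+3 tally is exposed. The other is that the lost DLT would turn 1 of 3 into 0 of 3 and open the Randomized Phase. Reaching 3 evaluable participants would need a replacement, which the protocol allows only for shortfalls not caused by a DLT. The written rules stall at 2 evaluable participants.

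The conclusion rests on the visible text. SAP 4.1.1 is partly redacted and the 3+3 schematic is not shown. The run-in rule may well be meant as the stricter one.

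**What to change.** 1. Reconcile the DLT section of Protocol 5.1.2.1 with 8.1.1, and with 7.4.4.1 for Grade 3 lymphopenia, which that section exempts from dose omission. One precedence sentence and a cross-reference would do. They should say which section governs Grade 3 AST or ALT elevation, Grade 4 neutropenia of exactly 7 days, and leukopenia or lymphopenia recorded as an AE, and whether the residual line reaches hematologic events without their own line. Which events count as DLTs or stop treatment is for the sponsor and investigators.
2. In Protocol 5.1.2.1 and SAP Table 6.3-1, base the first route to evaluability on having experienced a DLT in the 4-week period, whether or not treatment was discontinued. Every observed DLT in the window then enters the 3+3 tally, whichever section the site followed.

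The cost is wording only: one sentence, one cross-reference, and one clause in each document. No participants, visits or assessments are added, and no sample-size figure changes.
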